Hip Muscle Activity: Surface electromyography (EMG) data will be recorded at 1200Hz (Motion Labs, Baton Rouge, LA) from six muscles (adductor magnus, rectus femoris, tensor fascia latae, gluteus medius, biceps femoris long head, and gluteus maximus) on the residual limb of prosthesis users walking at preferred, slow (-25%), and fast (-25%) speeds on a force-sensing treadmill (Treadmetrix, Salt Lake City, UT). Speeds will be maintained across test sessions (baseline, 8-, and 42-weeks). Ground reaction forces will be recorded simultaneously at 1200Hz to identify gait cycle events. Neonatal electrodes, placed according to the Surface Electromyography for the Non-Invasive Assessment of Muscles (SENIAM) standards, will be

used to accommodate the collection of in-socket EMG signals. Raw EMG signals will be: i) band-passed filtered (10-500Hz) to remove non-muscle frequencies, ii) high-pass filtered (50Hz) to remove motion artifact, iii) notch-filtered (59.5-60.5Hz) to remove ambient power line noise, iv) amplitude normalized to the peak of the subject's ensemble average during fast walking on visit 1, and v) time normalized to 100% gait cycle (i.e., initial contact to initial contact). Activity of residual limb hip muscles will be characterized by onset and offset times, as well as the integrated area and peak activity. Onset and offset times will be identified from processed EMG signals using a Teager-Kaiser energy operator signal-conditioning algorithm, and referenced to initial contact. This procedure detects EMG burst boundaries with greater accuracy than other methods. The integrated area and peak activity of EMG bursts will be calculated by applying trapezoidal integration and thresholding techniques to linear EMG envelopes generated from full wave rectification and low-pass filtering (10Hz cut-off) of processed EMG signals. Muscle activity metrics will be averaged over a minimum of 10 strides per participant. EMG processing and analyses will be performed using custom Matlab[™] (MathWorks Inc., Natick, MA) routines.

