Aim 2: Test whether socket design alters hip muscle function among lower limb prosthesis users. We hypothesize that walking with different socket designs will: i) require different residual limb hip muscle activity, as evidenced by greater peak muscle activity, as well as altered onset and offset times, and ii) result in short- and long-term gains in residual limb hip muscle strength and endurance, as evidenced by an increase in average peak torque, rate of torque development, and resistance to fatigue. To test these hypotheses electromyographic signals will be recorded from hip muscles on the residual limb of unilateral lower limb prosthesis users walking at a range of speeds. Hip muscle strength and endurance will be measured using a motor-driven dynamometer. Assessments will be made at baseline in established wearers of an ischial containment socket, and then again at eight and 42-weeks after being fit with a sub-ischial socket. Step count activity data will be collected to determine the extent to which gains in residual limb hip muscle strength and endurance are due to changes in hip muscle activation versus an increase in physical activity.

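### The fast walking speed carries the same -25% offset as the slow speed, so as written there is no fast condition, and that condition is also the EMG amplitude reference

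*Combined protocol and SAP*

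**What the plan says.** The Hip Muscle Activity paragraph of section 6.0 records surface EMG from six residual-limb muscles on a treadmill, with participants "walking at preferred, slow (-25%), and fast (-25%) speeds". It keeps these speeds the same at baseline, week 8 and week 42. Signals are to be "amplitude normalized to the peak of the subject's ensemble average during fast walking on visit 1", and activity is then "characterized by onset and offset times, as well as the integrated area and peak activity".

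Section 3.0, Aim 2, describes the recordings as coming from "unilateral lower limb prosthesis users walking at a range of speeds". Its first hypothesis is that a different socket requires different muscle activity, "as evidenced by greater peak muscle activity, as well as altered onset and offset times".

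Section 12.0 summarizes Aim 2 with means, 95% confidence intervals and effect sizes such as Cohen's d, and limits enrollment to 10. No other section gives a figure for the fast speed.

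**The concern.** A condition called fast cannot sit 25% below preferred, and two separately named conditions cannot usefully share one speed. The figure is a working setting with three uses: it sets the treadmill, it is carried unchanged through all three visits, and it defines the walking condition whose visit 1 peak is the denominator for EMG amplitude. A baseline error would therefore repeat at weeks 8 and 42.

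At stake are the fast-speed EMG data and the units in which peak and integrated area are pooled across participants.

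**Working it through.** The offset is a design setting, so the plan has no derived figure to reproduce. The check is direct arithmetic followed by the algebra of the normalization.

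**Inputs**
- Slow offset -25% and fast offset -25%: section 6.0, Hip Muscle Activity.
- Base for the percentages: preferred speed. This is implied, not stated, and is taken as an assumption.
- Reference: one value per participant and muscle, the visit 1 fast-walking peak (section 6.0).
- Summaries: group mean, 95% confidence interval, Cohen's d (section 12.0).

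**1. Speeds as printed.** Speed = preferred × (1 + offset).
- Slow = 1 - 0.25 = 0.75 of preferred.
- Fast = 1 - 0.25 = 0.75 of preferred.
- Fast/slow = 0.75/0.75 = 1.00.

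The tested range is 0.75 to 1.00 of preferred: 25 percentage points and two distinct speeds.

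**2. Speeds with a positive fast offset x.** The documents give no x, so these values are illustrations. Fast/slow = (1 + x)/0.75.
- x = 10%: 1.10/0.75 = 1.47.
- x = 25%: 1.25/0.75 = 1.67. The range becomes 0.75 to 1.25, or 50 points and three speeds.

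**3. Effect on one participant.** Let A1 and Av be a participant's un-normalized peak (or area) for one muscle at one speed, at visit 1 and at visit v, and let R be the reference. The normalized values are A1/R and Av/R.
- Relative change = (Av/R - A1/R)/(A1/R) = (Av - A1)/A1. R cancels.
- R is positive, so the direction of the change does not depend on it either.

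**4. Effect on the pooled summaries.** The change in normalized units is (Av - A1)/R, and R differs between participants. Suppose moving from one reference speed to another multiplies participant i's reference by k_i, so that the change is divided by k_i.
- If k_i is the same in everyone, the group mean and its confidence limits are all divided by that constant, and Cohen's d is unchanged.
- If k_i varies, the participants are reweighted, and the mean, the interval and d can all move.

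The documents give no value or spread for k_i, so the size of this effect cannot be stated.

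**5. Effect on timing.** Onset and offset are times relative to initial contact. Multiplying a signal by a constant does not move them, provided the detection threshold scales with the signal (an assumption; the threshold is not given). What would be missing is timing at a truly fast speed.

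**The case against.** The strongest reply is that this is an obvious sign slip. The finding rests on one character in machine-read text, and a plus sign read as a minus cannot be excluded. The condition's label and the Aim 2 wording show that a speed above preferred was intended, and nothing in the documents shows that the study was or will be run at the printed figure. All of that stands, and it lowers the severity.

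It does not dispose of the point. The intended increment cannot be recovered from the text, since +25% is only an inference from symmetry. Section 10.0 also has each session checked for consistency with the protocol, with departures reported to the IRB and the data deleted. Staff who sensibly set a speed above preferred would depart from the written text; staff who follow it would collect a second slow condition.

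A reader might go further and infer that the error spoils every EMG amplitude for six muscles at three visits, and with it the first Aim 2 hypothesis. The documents do not support that:
- The reference is one fixed visit 1 value per participant and muscle, and Aim 2 compares each participant with their own baseline, so it cancels from relative change (step 3).
- Recordings at preferred and slow speeds remain valid. If the raw signals are kept, they could be rescaled to another condition. Section 8.0 stores muscle activity data without saying whether in raw form.
- The powered comparison is untouched. The 20 per group in Aim 1 rests on dynamometer strength and endurance, whereas the EMG hypothesis sits in a descriptive pilot of 10.

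Rescaling cannot, however, supply data at a speed nobody walked.

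**Conclusion.** Wrong as written: an internal inconsistency of moderate to minor severity. The printed offsets make fast identical to slow (ratio 1.00) and slower than preferred, against both the label and the Aim 2 description.

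If the text is followed, two consequences hold: the distinct fast condition is lost at all three visits, and pooled normalized peak and area values change in scale and between-participant weighting. The second is of unknown size.

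The conclusion assumes that the percentages are relative to preferred speed and that the source file prints the same minus sign as the text reviewed.

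**What to change.** 1. Check the sign against the source file.
2. If the minus sign is there, replace the fast offset with the sponsor's intended value above preferred speed, and say that both percentages are relative to preferred. Use +25% only if symmetry with the slow condition was intended.
3. Confirm that the corrected visit 1 fast condition is the EMG amplitude reference. Recording each participant's visit 1 speeds in m/s would make it plain which speeds are reused at weeks 8 and 42; this is helpful but optional.
4. If any sessions have already been run, report the speed actually used for the fast condition.

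The cost is a change of a character or a phrase, plus whatever IRB handling a protocol correction needs. No added visits, measurements or participants are required.

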12.0 Statistical Considerations

Descriptive statistics: Measures of central tendency and variation will be used to describe participant characteristics, and all study variables (e.g., balance and mobility tests, muscle strength). Normality, homogeneity of variance, and multicollinearity will be evaluated using the Shapiro-Wilk test, Levene's test, and, Pearson's r (r<.90) respectively. If assumptions are met data will be analyzed with parametric tests, otherwise non-parametric tests will be used. Statistical analyses will be performed using SPSS 25 (Chicago, IL).

Aim 1: A 2-way mixed-MANCOVA (multiple analysis of covariance), or non-parametric equivalent, will be used to test for statistically significant differences in strength and endurance between legs (prosthetic, intact, and control) as well as across muscle groups while controlling for potential covariates (e.g., residual limb length, etiology). Multiple linear regression will be used to determine how much variation (i.e., difference) in balance and mobility outcomes (e.g., Four Square Step Test; physical activity) among transfemoral prosthesis users can be explained by differences in hip muscle strength and endurance.

Aim 2: As a pilot study, descriptive analyses including measures of central tendency (mean) and dispersion (95% confidence intervals), along with effect sizes (e.g., Cohen's d, common

language effect size), will be used to evaluate changes in residual limb hip muscle activity, strength, between test sessions while controlling for covariates. Correlation analyses will be used to determine if any observed changes in hip muscle strength can be attributed to changes in hip muscle activity (i.e., EMG) or physical activity (i.e., step count).

Power Analysis: Choosing a power of 0.80 and a type I error rate (α) of 0.05, pilot data from lower prosthesis users (n=2) and able-bodied persons (n=2) estimate that a sample of 20 people per group will be sufficient to identify differences (p<0.05) in hip muscle strength and endurance between the residual limb, intact limb, and able-bodied persons using a mixed analysis of variance (ANOVA) (Aim 1). As a pilot study, enrollment in Aim 2 will be limited to 10 unilateral lower limb prosthesis users.

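### Averaging follow-up EMG amplitude as a raw ratio to each person's visit 1 fast-walking peak biases the expected mean upward, and Cohen's d has no stated standardiser; log ratios cure both

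*Combined protocol and SAP*

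**What the plan says.** Section 6.0 (Hip Muscle Activity) scales EMG amplitude to the peak of each participant's "ensemble average during fast walking on visit 1". The divisor is one value per participant, measured once, and it is applied to baseline, week 8 and week 42 alike. Activity is then "characterized by onset and offset times, as well as the integrated area and peak activity", and "Muscle activity metrics will be averaged over a minimum of 10 strides per participant". The text does not say whether peak activity is read from the ensemble average or is the mean of single-stride peaks.

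Section 3.0 (Aim 2) expects a different socket to require different hip muscle activity, "as evidenced by greater peak muscle activity" among other signs. Section 12.0 describes Aim 2 as a pilot limited to 10 prosthesis users and evaluates change between sessions by "measures of central tendency (mean) and dispersion (95% confidence intervals), along with effect sizes", with Cohen's d and the common language effect size as examples. It names no log scale, no geometric mean and no standardiser for d.

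**The concern.** A follow-up amplitude expressed this way is a ratio whose denominator carries measurement error. The arithmetic mean of such ratios does not centre on 100% when nothing has changed; it centres above it. The hypothesis is for greater peak activity, so the bias favours the hypothesis.

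The same divisor also removes most or all of the spread in the baseline fast-speed peak. Cohen's d for that measure then depends heavily on which SD is chosen, and the plan does not choose. With n=10 and no test planned for Aim 2, the estimates and effect sizes are the reported result for EMG amplitude, so how they are formed matters.

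**Working it through.** No figure in the plan depends on EMG normalisation, so there is nothing to reproduce. The documents supply the divisor, the arithmetic mean, the direction of the hypothesis and n=10. Between-visit variability is not given and is assumed below.

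**1. Direction of the bias.** Let X1 and X2 be a participant's fast-speed peaks at visit 1 and follow-up. If nothing changes and the visits are exchangeable, E[X2/X1] = E[X1/X2]. A positive number and its reciprocal average at least 1, so E[X2/X1] exceeds 1 whenever the visits differ at all. No distributional assumption is needed.

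**2. Size.** Assume the log ratio is normal with mean 0 and SD s. Then E[ratio] = exp(s²/2), SD[ratio] = exp(s²/2) × √(exp(s²) − 1), and the 95% half-width at n=10 is about 2.262 × SD/√10.

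| s | Expected mean ratio | SD of ratio | CI half-width |
|---|---|---|---|
| 0.2 | exp(0.020) = 102% | 0.21 | 15 points |
| 0.3 | exp(0.045) = 105% | 0.32 | 23 points |
| 0.4 | exp(0.080) = 108% | 0.45 | 32 points |

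The geometric mean is centred on 100% throughout. In terms of a per-session CV, E[ratio] = 1 + CV², which is 101% at CV 0.1 and 125% at CV 0.5. This is a wider range of assumptions than the table, because s² = 2 ln(1 + CV²) puts CV 0.1 at s = 0.14 and CV 0.5 at s = 0.67. In simulation over that wider range (n=10, no true change), the sample mean exceeded 100% in 58% to 80% of trials.

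**3. Other speeds.** At slow speed the baseline is not fixed at 100%, but its error is tied to the divisor if session error (electrode placement, for example) is common to all speeds. With a session CV of 0.3 and no true change, the simulated false relative rise was 0%, 4% and 8% when 0%, 50% and 90% of the session error variance was shared.

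**4. Baseline variance.** If peak is read from the ensemble average, every baseline fast-speed value is exactly 100% and its SD is 0. If stride peaks are averaged, the simulated baseline was about 101% (SD 1) with little timing jitter and about 112% (SD 9) with more.

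**5. Effect on d.** With baseline SD 0, the SD of change equals the follow-up SD, and the pooled SD is √((0 + SD²)/2) = SD/1.41. A d standardised by the baseline SD is undefined. A d standardised by the pooled SD is 1.41 times the one standardised by the SD of change. For a true +10% change and s = 0.3, the mean ratio is 1.10 × 1.046 = 1.151 and its SD is 1.10 × 0.321 = 0.353:

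- pooled SD: 0.151/(0.353/1.41) = 0.60
- SD of change, raw ratio: 0.151/0.353 = 0.43
- SD of the log change: ln(1.10)/0.3 = 0.095/0.3 = 0.32

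The 0.43 is free of the zero-variance effect but still contains the ratio bias. Only the 0.32 is free of both.

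**The case against.** The strongest reply is that the d problem belongs to a formula the plan does not contain. Section 12.0 names no standardiser, Section 6.0 calls Aim 2 a within-subjects study, and with the SD of change the lack of baseline variance does no harm. That stands: the inflation is conditional on a baseline or pooled SD. It applies to peak activity at fast speed, is exact only if peak is read from the ensemble average, and does not touch onset and offset times or, as such, integrated area.

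It is also fair that the bias in the mean is small beside the sampling error at n=10, that its size rests on assumed variability, and that no type I error claim depends on it. Even so, the bias is systematic, and a wide interval placed around a shifted centre does not correct it. The non-parametric fallback in Section 12.0 does not correct it either, because changing the test leaves the reported mean, interval and d as they were.

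Three stronger readings are tempting and unsupported:

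- **A reader might infer that the follow-up mean will exceed 100% regardless.** It is expected to, but in 20% to 42% of the simulated null samples it did not.
- **A reader might infer that a later trial would be undersized.** The documents never say that these EMG effect sizes will be used to size one.
- **A reader might infer that d for every Aim 2 outcome should use the SD of change.** For paired data with equal variances, d on the SD of change equals d on the pooled SD divided by √(2(1 − r)). It is therefore larger whenever the between-visit correlation r exceeds 0.5 (1.58 times at r = 0.8). Nothing in the EMG argument carries over to torque.

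**Conclusion.** The point holds for EMG amplitude. Followed as written, the plan gives an expected fast-speed follow-up mean of about 102% to 108% under no true change, for an assumed log-ratio SD of 0.2 to 0.4. The shift is toward the hypothesis and can reach the other speeds when session error is shared. Its direction needs only exchangeable visits; its size rests on the assumed SD and a lognormal model.

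The plan also leaves open a choice that makes d for fast-speed peak undefined or very large, up to 1.41 times the change-based value, or unaffected by the missing baseline variance. This is a fault in how the ratios are summarised. Whether visit 1 is a sound reference at all is a separate question. The change is worth making because it is nearly free, but it concerns one family of outcomes in a descriptive pilot of 10.

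**What to change.** In Section 12.0 (Aim 2), specify that EMG peak activity and integrated area are analysed as within-person log ratios, week 8 to baseline and week 42 to baseline, at each speed. Report the geometric mean ratio with its t-based 95% confidence interval and the SD of the log change. For these EMG amplitude outcomes, standardise any d by the SD of the within-person log change.

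The normalisation in Section 6.0 can stay: within a person and speed the visit 1 divisor cancels, since (X2/F1)/(X1/F1) = X2/X1. Section 6.0 should add one sentence saying whether peak activity comes from the ensemble average or from averaged stride peaks.

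The cost is a few lines of SAP wording and a log transform, with no new data or visits. The downside is that results are read as ratios and the EMG estimates may look slightly less favourable. No change to the effect sizes for strength or endurance, or to the common language effect size, follows from this point.

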7.0 Expected Risks/Benefits

Foreseeable, potential risks for prosthesis users and able-bodied controls participating in this study include: a) fatigue resulting from long periods of standing or walking, b) injury from mechanical failure of the equipment (e.g., treadmill, motorized dynamometer), c) falling during administration of the study protocol, d) electrical shock associated with recordings of

electromyograms (EMG), e) irritation to the skin from medical grade tape used to attach sensors to the body, or f) embarrassment. The risk associated with these events is expected to be low. We have attempted to reduce known potential risks. We do not know of alternative procedures that can reduce these risks and provide the same information. The safety precautions associated with the potential risks are as follows:

- a) Loss of balance and falls: All study personnel will undergo falls training led by the PI. This training will familiarize them with appropriate spotting techniques to catch a participant if they begin to fall.
- b) Fatigue: The test sessions may last up 3 hours, however, only 90 minutes are dedicated to study procedures. This duration may nonetheless be fatiguing to some participants. The majority of the time is devoted to participant preparation and instrumentation, a large part of which is done while the participant is either sitting or lying down. We will enforce sitting breaks of at least 5 minutes every 20 minutes of experimentation. The breaks will only end with the participant's consent and participants will be continually monitored during testing by the evaluator and trained assistants for fatigue and instability.
- c) Mechanical injury: The treadmill and motorized dynamometer are physically limited by the motor torque and cannot deliver excessively large, injury-causing perturbations. They are equipped with limit switches that shut down power if they reach near the end range of their capabilities. Software limits further limit uncontrollable movements of the treadmill and dynamometer. There is an emergency stop button next to the experimenter and on the treadmill as well as the dynamometer for participants. Additionally, all equipment will be inspected for safety as part of the set up routine for each data collection session.
- d) Electrical shock: The risk of electrical shock is extremely low and limited to non-injurious levels of current and voltage. Our electromyography equipment is a telemetered unit powered by a standard 9-volt battery. Therefore if a malfunction were to occur, any electrical shock produced would be extremely mild. Our equipment is available commercially (Motion Lab Systems) and no participants have experienced any electric shock or tingling sensations due to current flow.
- e) Skin irritation: Some participants are sensitive to the adhesive used in medical grade tape. This can result in temporary irritation such as redness or itchiness in areas where tape has contacted the skin. We will ask participants if they have known tape sensitivity before the experiment begins. The supply of tapes and adhesives we use are hypoallergenic medical grade that are commonly used in hospitals. In the PI's experience in and around the testing of hundreds of human participants with similar supplies, only one case of tape allergy has occurred. This one incident left no permanent injury to the participant.
- f) Discomfort/embarrassment: To reduce potential discomfort or embarrassment in answering health related questions all questionnaires will be completed in a private room. If participants do not want to answer particular questions they do not have to. To reduce embarrassment of being videotaped all recordings will be taken from behind. Faces will not be recorded. Any identifiable marks will be blurred if videos are ever used

in a presentation. Video recording is optional. To minimize any potential embarrassment due to loss of confidentiality all records of participation that included information about participants will be coded. Names and unique subject IDs do not appear on the same documents. The data from this study cannot be traced directly back to participants. Additionally, all documents from this research will be kept in a locked file cabinet by the study team. We are the only ones with access to these documents.

We do not anticipate that participants will receive any direct benefit from participating in the study. The study is not being conducted to improve their health condition. It is hoped that knowledge gained from this research may benefit other lower limb prosthesis users in the future by providing an approach to increase and/or prevent the loss of residual limb hip muscle strength.

